## **9.4        Exclusion of Women, Minorities, and Children (Special Populations)**

This trial will be inclusive of female adults who meet the Participant Inclusion/Exclusion Criteria, regardless of religion or ethnic background. Should the outcome of this trial be deemed acceptable, additional trials may be initiated in other populations.

Persons who are unable to fully participate in the study due to an inability to provide informed consent will not be enrolled, for example non-English speakers, children, illiterate or non-writing individuals. This exclusion is to ensure participants who cannot fully understand the implications of study participation due to language or cognitive barriers are not recruited.

## **9.5        Participant Confidentiality**

Participants will have code numbers and will not be identified by name. Participant confidentiality is strictly held in trust by the participating site PIs, their study staff, and the sponsor(s) and their agents. This confidentiality includes the study protocol, documentation, investigation data, participant’s clinical information, testing of biological specimens, and all other information generated during participation in the study. No information concerning the study, or the data generated from the study will be released to any unauthorized third party without prior written approval of the DMID. Authorized third parties include OHRP or other government agencies as part of their duties, the FDA, single IRB, NIH, study staff, study monitors, Toltec, and designees. Participant confidentiality will be maintained when study results are published or discussed in conferences.

All information provided by the sponsor and all data and information generated by the participating site as part of the trial (other than a participant’s medical records) will be kept confidential by the site PI and other study personnel to the extent permitted by law. This information and data will not be used by the site PI or other study personnel for any purpose other than conducting the trial. These restrictions do not apply to: (1) information that becomes publicly available through no fault of the site PI or other study personnel; (2) information that is necessary to disclose in confidence to an IRB solely for the evaluation of the trial; (3) information that is necessary to disclose in order to provide appropriate medical care to a study participant; or (4) study results that may be published as described in [Section 15](#). If the

---

confidentiality provisions in the executed site contracts for the conduct of this trial are inconsistent with this statement, the site contract's confidentiality provisions shall apply rather than this statement.

The study monitor, or other authorized representatives of the sponsor, or governmental regulatory agencies such as the FDA may inspect all documents and records required to be maintained by the site PI. This includes, but is not limited to, medical records (office, clinic, or hospital) and pharmacy records for the participants in this study. The participating sites will permit access to such records.

## **9.6 Certificate of Confidentiality**

To protect privacy, we have received a Certificate of Confidentiality (CoC). With this CoC, the participating sites cannot be forced to release information that may identify the research participant, even by a court subpoena, in any federal, state, or local civil, criminal, administrative, legislative, or other proceedings. The participating sites will use the CoC to resist any demands for information that would identify the participant, except as explained below.

The CoC cannot be used to resist a demand for information from personnel of the United States Government that is used for auditing or evaluation of federally funded projects, like this study, or for information that must be released in order to meet the requirements of the FDA.

A CoC does not prevent the participant from voluntarily releasing information about themselves or their involvement in this research. If any person or agency obtains a written consent to receive research information, then the researchers may not use the Certificate to withhold that information.

The CoC does not prevent the participating sites from reporting without the participant's consent, information that would identify the participant as a participant in the study regarding matters that must be legally reported including: child and elder abuse, sexual abuse, or wanting to harm themselves or others.

The release of individual private information or specimens for other research will only occur if consent was obtained from the individual to whom the information, document, or biospecimen pertains, or for the purposes of other research that is in compliance with applicable Federal regulations governing the protection of human participants in research.

---

## **9.7 Costs, Participant Compensation, and Research Related Injuries**

There is no cost to participants for taking part in this trial.

Procedures and treatment for clinical care may be billed to the participant, participant's insurance or third party. Participants may be compensated for their participation in this trial.

Compensation will be in accordance with the local IRB's policies and procedures, and subject to IRB approval.

If it is determined by the site PI that an injury occurred to a participant as a direct result of the tests or treatments that are done for this trial, then referrals to appropriate health care facilities will be provided to the participant. Study staff will try to reduce, control, and treat any complications from this trial. Immediate medical treatment may be provided by the participating site. No financial compensation will be provided to the participant by the NIAID, NIH, or by the participating site for any injury suffered due to participation in this trial.

---

## 10 STATISTICAL CONSIDERATIONS

### 10.1 Study Hypotheses

The primary objective of the study is to evaluate the clinical efficacy of a twice-weekly application of the TOL-463 vaginal insert for the suppression of BV following successful induction with oral metronidazole or other CDC-recommended BV treatment in women with a history of recurrent BV. Clinical efficacy (suppression) is defined by clinical cure (see [Section 3.3.1](#)). There is one planned hypothesis test with respect to the primary outcome measure. The hypothesis test compares the proportion of participants with recurrent BV by V4 between treatment arms. The null hypothesis for the comparison is that there is no difference in cure rates between treatments, with a two-sided alternative. The test will be conducted using the Pearson Chi-Square test at the 5% two-sided significance level.

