### 10.2 Sample Size Considerations

As detailed in [Section 10.5](#), efficacy analyses will be performed in an evaluable subset of the enrolled population; this subset was used to derive the study's sample size. Assuming a 40% BV recurrence rate among women receiving placebo and a 50% reduction in recurrence among women treated with TOL-463 (i.e. 20% recurrence rate among TOL-463 recipients) and a 1:1 allocation ratio between treatment arms, a sample size of 200 evaluable participants will provide at least 85% power using the Chi-Square Test. Assuming 80% of enrolled participants will be evaluable for the primary analysis, the enrollment target is set to 250 to achieve 200 evaluable participants.

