6.4. Covariates and Subgroups

The protocol does not define any formal subgroup analyses, and the study is not adequately powered to perform subgroup analyses.

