8. EFFICACY EVALUATION

8.1. Primary Efficacy Analysis

The primary efficacy endpoint for the final analysis is the proportion of subjects with recurrent BV by Test of Cure (TOC, Visit 4 window: Day 85-91) as defined in section 3.3, and in section 6.5 for missing BV status by TOC.

The number of subjects, the proportion of subjects with RBV up to and including V4 will be presented overall and by treatment group with two-sided 95% Wilson confidence interval (no continuity correction). In addition, the difference in proportions between the TOL-463 Vaginal Insert arm and the Placebo group and 95% Newcombe confidence intervals (based on the Wilson CI for the individual proportions) will be presented. See [Table 6](#).

The pseudocode to fit the above analyses is below:

```
proc freq data=dataset;
  Table treatment*cure /chisq riskdiff(Newcombe) binomial(wilson) out=output
  alpha=.05;
run;
```

The primary efficacy analysis will be performed in the mITT population ([Table 6](#)). As a sensitivity analysis, the primary endpoint will additionally be assessed among all subjects in the mITT population except those terminated early due to study disruptions from the COVID-19 pandemic ([Table 7](#)). Analysis of the primary outcome measure will be repeated in the PP analysis population (secondary analysis of primary outcome). See [Table 8](#).

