9.1.3. Gynecologic and Sexual History

The number of times the subject had BV in the past 12 months obtained at screening visit will be presented by treatment group and clinical site in the demographics tables ([Table 23](#) and [Table 24](#)). Individual subject listings of screening and baseline ([Listing 13](#)) and follow-up ([Listing 14](#)) sexual history for all enrolled subjects will be presented.

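### The primary between-arm comparison is valid but uses neither site nor prior-year BV episode count; a pre-specified adjusted risk difference beside it would cost little and could be modestly more precise

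*Protocol*

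**What the plan says.** - **Test.** Protocol 10.1 plans one hypothesis test of the primary outcome: "The test will be conducted using the Pearson Chi-Square test at the 5% two-sided significance level".
- **Estimate.** SAP 8.1 adds "the difference in proportions between the TOL-463 Vaginal Insert arm and the Placebo group and 95% Newcombe confidence intervals". Its pseudocode is a treatment-by-cure frequency table with no strata and no model, and the shells of Tables 6 to 8 follow it.
- **Covariates.** SAP 6.4 is headed Covariates and Subgroups but names no covariate. Its whole content is "The protocol does not define any formal subgroup analyses, and the study is not adequately powered to perform subgroup analyses".
- **Episode count.** SAP 9.1.3 covers "The number of times the subject had BV in the past 12 months obtained at screening visit". It is summarised by site and by arm in Tables 23 and 24 and listed in Listing 13. No efficacy analysis uses it.
- **Site.** Randomisation is stratified by site alone (Protocol 10.3.1, SAP 4.4.3). SAP 6.7 pools the sites, expects no centre effects and gives an exploratory by-site tabulation (Table 13). Site is in no between-arm model.
- **Supportive analyses.** Protocol 10.5.4.3 promises to explore recurrence by baseline characteristics. Apart from Table 13 the SAP contains nothing of this kind, and SAP 12 plans no further analyses.

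**The concern.** Eligibility rests on recurrence history: at least two episodes in the past year besides the current one (Protocol 5.1.1.1). The endpoint is the next recurrence. It is therefore plausible that women with more prior episodes recur more often, although neither document gives any figure for this.

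If the association exists, two things follow. The crude difference carries outcome variation that a baseline value already in the database could remove. And since nothing in the design balances episode count, a chance difference between arms stays in the crude estimate. Table 24 would display such a difference, but no rule says what to do about it, so any later adjustment would be post hoc. SAP 5 reports early closure without giving the achieved sample size. Chance imbalance tends to be larger in a smaller trial.

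**Working it through.** **1. Reproduce the plan's own power.** Inputs from Protocol 10.2: "Assuming a 40% BV recurrence rate among women receiving placebo"; "20% recurrence rate among TOL-463 recipients"; "1:1 allocation ratio between treatment arms"; and "a sample size of 200 evaluable participants will provide at least 85% power using the Chi-Square Test".

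- Null SE = sqrt(2 × 0.30 × 0.70 / 100) = 0.0648
- Alternative SE = sqrt((0.40 × 0.60 + 0.20 × 0.80) / 100) = 0.0632
- Power = Φ((0.20 − 1.96 × 0.0648) / 0.0632) = Φ(1.15) = 87.6%

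The claim of at least 85% holds; 186 evaluable women would reach 85%. Enrolment is 200 / 0.80 = 250, as stated.

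**2. Set up the adjusted estimate.** Fit a logistic model of recurrence on arm and episode count. Predict each woman's risk under each arm, average over all women, and take the difference (g-computation). The SE comes from the influence function.

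The prognostic strength of the count is an assumption, shown as an odds ratio (OR) per SD from 1.0 to 2.0. The simulated count has minimum 3, mean 4.5 and SD 1.2 (also assumed), with marginal recurrence 40% and 20%, 100 per arm and 6,000 trials per scenario. Site was not simulated.

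**3. Results.** The approximate 95% CI half-width is 1.96 × 0.0632 × sqrt(variance ratio). The shift is the slope of the crude difference on the between-arm covariate difference, times 0.2.

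| OR per SD | Adjusted/crude variance | CI half-width, points | Slope | Shift at 0.2 SD, points | Rejection, crude vs adjusted |
|---|---|---|---|---|---|
| 1.0 | 1.00 | 12.4 | −0.008 | about 0 | 88.0% vs 87.9% |
| 1.25 | 0.99 | 12.3 | 0.056 | 1.1 | 87.5% vs 88.1% |
| 1.5 | 0.97 | 12.2 | 0.077 | 1.5 | 87.9% vs 89.1% |
| 2.0 | 0.90 | 11.8 | 0.143 | 2.9 | 88.3% vs 91.2% |

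Monte Carlo error of the rejection rates is about 0.4 points. The adjusted estimate showed almost no dependence on imbalance. A second run (3,000 trials per scenario) gave variance ratios of 0.97 and about 0.93, and shifts of 1.6 and 2.6 points, at OR 1.5 and 2.0. The upper end of the shift is therefore 2.6 to 2.9 points.

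**4. How often such an imbalance arises.** The SD of the between-arm difference, in covariate SDs, is sqrt(2/n).

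- 100 per arm: 0.141, so P(|difference| > 0.2) = P(|Z| > 1.41) ≈ 16%.
- 60 per arm (illustrative, as the achieved size is not stated): 0.183, so P(|Z| > 1.10) ≈ 27%.

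**5. Validity.** With 30% recurrence in both arms and 100 per arm, the crude test rejected in 4.8% to 5.8% of trials and the adjusted one in 4.9% to 5.9%.

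**6. Less favourable conditions.** The history may be self-reported (Protocol 5.1.1.1), and SAP 6.5 counts undetermined outcomes in the mITT population as failures. With a floored count on the log scale, reliability 0.6 and 15% to 20% of outcomes set to failure at random (all assumed), the variance ratio moved from 0.97 to 0.99–1.00 at OR 1.5, and from 0.93 to 0.97–0.98 at OR 2.0.

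**The case against.** The strongest reply is that nothing is wrong. Randomisation makes the crude test valid; protocol, sample size and SAP code agree on it; and the power is as stated. The benefit of adjusting depends on an association that the documents never mention, and under realistic measurement and missing-data conditions it shrinks to very little. All of this stands.

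The choice of covariate can also be questioned. Pre-treatment pH, Amsel count and Nugent category at V1 are available too, and no evidence in the documents ranks episode count above them. The count is also not fully defined: the Protocol Summary's three diagnoses include the one at screening, Protocol 5.1.1.1 counts two previous episodes, and SAP 9.1.3 does not say which number is recorded. These points stand as conditions on the fix. In very small samples the influence-function SE may be slightly anti-conservative: with a non-prognostic covariate at 30 per arm, the adjusted test rejected 6.0% against 4.6% for Pearson.

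A reader might infer three stronger things:

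- *The primary test is biased or has the wrong error rate.* Neither its randomised basis nor the simulation supports that.
- *Precision is known to be lost.* The documents give no prognostic strength, and at OR 1.0 there is no loss.
- *Adding the adjusted estimate would raise the trial's power.* It would not, because Pearson stays the protocol-specified test. The rejection rates in the table only illustrate precision.

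What survives is narrower. Stating the adjusted estimate in advance is nearly free, and without it any response to an imbalance seen in Table 24 would be post hoc.

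**Conclusion.** This is a worthwhile improvement to the plan; it does not correct an error. The test and sample size are sound. Leaving out episode count costs between nothing and about 10% of the variance of the risk difference at 100 per arm, or at most about 0.6 points of CI half-width (12.4 to 11.8). It leaves a 0.2 SD chance imbalance worth about 0 to 3 points in the crude estimate, against a planned effect of 20. These sizes rest on assumed ORs of 1.0 to 2.0 per SD, and the precision gain is smaller with self-report error and missing-as-failure. The contribution of site has not been quantified. Early closure makes chance imbalance more likely, but by how much cannot be said without the achieved sample size.

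**What to change.** Keep the Pearson chi-square as the protocol-specified test. In SAP 6.4 and 8.1, before unblinding:

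1. Pre-specify a logistic model of the primary outcome on arm, site and log(number of BV episodes in the past 12 months).
2. State whether the count includes the screening episode.
3. Report the standardised (g-computation) risk difference with a robust 95% CI, giving the SE formula, as the named adjusted estimate beside the crude one in Table 6 (mITT) and Table 8 (PP).

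If treatment codes have already been opened, label the analysis post hoc.

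The cost is a few lines of SAP text and one extra row in two tables. No new data are needed. Protocol 10.5.4.1 already leaves further sensitivity and corroborative analyses to the SAP, so no protocol amendment is needed. The small downside is a second estimate to report and explain.

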### 10.2 Sample Size Considerations

As detailed in [Section 10.5](#), efficacy analyses will be performed in an evaluable subset of the enrolled population; this subset was used to derive the study's sample size. Assuming a 40% BV recurrence rate among women receiving placebo and a 50% reduction in recurrence among women treated with TOL-463 (i.e. 20% recurrence rate among TOL-463 recipients) and a 1:1 allocation ratio between treatment arms, a sample size of 200 evaluable participants will provide at least 85% power using the Chi-Square Test. Assuming 80% of enrolled participants will be evaluable for the primary analysis, the enrollment target is set to 250 to achieve 200 evaluable participants.

### 10.3 Treatment Assignment Procedures

#### 10.3.1 Randomization Procedures

Participants will be randomized 1:1 to receive one of two treatments: TOL-463 vaginal inserts or Placebo vaginal inserts.

The list of randomized treatment assignments will be prepared by statisticians at the SDCC and included in the enrollment module of the Emmes' Internet Data Entry System (IDES). Advantage eClinical® will assign each participant to a blinded treatment number from the list after demographic and eligibility data have been entered. Each site will have a supply of blinded study drug kits pre-labeled with treatment numbers, each containing sufficient doses to treat a

---

participant for twelve weeks. The packaged study drug kits contain three, separate four-week kits to be dispensed to the participant at Enrollment V1 and Follow-ups V2 and V3 as applicable. Once a participant is assigned a treatment number, the corresponding kit will be distributed to the participant.

Instructions for using the enrollment module are included in the IDES User's Guide. Manual back-up randomization procedures are provided in the MOP for use in case the site temporarily loses Internet access, or the online enrollment system is unavailable.

The trial will use a site-stratified, permuted, blocked randomization scheme. Permuted blocked randomization is used to avoid the potential for serious imbalance in the number of participants assigned to each group, which can occur in simple randomization procedures.

### **10.3.2 Masking Procedures**

Participants, the study staff who dispense study drug and perform study assessments after study drug administration, data entry personnel at the sites, and laboratory personnel will be blinded to treatment assignment. The DSMB may receive efficacy data in aggregate and presented by treatment group, as specified in the DSMB charter. The DSMB may request to be completely unblinded to individual study drug assignments, as needed, to adequately assess SAEs. Refer to the MOP for unblinding procedures.

Study drug will be prepared at Fisher BioServices in blinded numbered kits. All kits will look identical and contain an identical number of inserts. Emmes will provide an unblinded list identifying the treatment identity (TOL-463 or placebo) in each kit to the Fisher staff responsible for preparing study drug kits. Clinicians, investigators, and all blinded staff will not have access to this list until after the trial has ended.

## **10.4 Planned Interim Analyses**

### **10.4.1 Interim Safety Review**

The study will be monitored to determine if any of the safety halting rules described in [Section 8.6](#) are met. The DSMB will meet and review safety data and enrollment data at specified times during the course of study and at a study closeout meeting, as defined in the [Section 8.7.2](#) and the DSMB Charter.

### **10.4.2 Interim Efficacy Review**

There are no planned interim efficacy analyses for this study.

## 10.5 Final Analysis Plan

A separate statistical analysis plan, (SAP) document will be generated which will contain the details of the analyses. This section outlines the major components of the analyses.

### 10.5.1 Analysis Populations

Safety Population: This analysis population includes all randomized participants who received at least one dose of study treatment.

Modified Intent-to-Treat (mITT) Population: This analysis population includes all randomized participants who are evaluable.

The mITT population will be used as the primary efficacy analysis population.

Per-Protocol (PP) Population: This analysis population includes all randomized participants who met all inclusion/exclusion criteria throughout the study, are evaluable (defined below), complied with the assigned IP, and returned to the study site for the TOC visit within the specified window (Visit 4 [Window: Day 85-91]) or were followed up to their diagnosis of recurrent BV.

Evaluable is defined as follows:

- Negative STI tests taken at baseline (*C. trachomatis*, *N. gonorrhoeae*, or *T. vaginalis*);
- For participants 21 years of age or older, documentation of or self-report of a normal or ASCUS HPV negative Pap test prior to screening, or a Pap smear performed at screening/enrollment with normal result

A participant is compliant with the study treatment if she misses  $\leq 2$  non-consecutive doses of IP per month, as assessed by participant memory aid and returned IP and packaging at each follow up visit (V2, V3, V4).

In the unlikely event of an error in randomization or IP administration (i.e., incorrect treatment), participants will be grouped by the treatment they actually received in safety analyses but will be grouped by their intended randomized assignment in efficacy analyses.

### 10.5.2 Baseline Characteristics

Baseline and demographic characteristics will be summarized overall and by treatment. For both continuous and categorical variables, appropriate summary statistics will be applied. For continuous variables, descriptive statistics will include the number of non-missing values, mean,

---

standard deviation, median, minimum, and maximum. For categorical variables, descriptive statistics will include counts and percentages per category.

